Corticolimbic Circuitry Dysregulation. Converging research suggests that both PTSD and AUD are associated with impaired prefrontal cortex (PFC) regulation of limbic brain regions, in particular the amygdala (AMY). The AMY plays a crucial role in threat perception, fear conditioning, emotional salience, and heightened memory for emotional events (Pitman et al., 2012). The PFC is responsible for disrupting habitual or compulsive behaviors that are not adaptive (e.g., compulsive alcohol use) (Pitman et al., 2012). Dysregulation of the PFC-AMY circuitry (i.e., lack of "top down" control) likely makes it difficult, therefore, to inhibit or modulate obsessive cognitions such as intrusive trauma-related memories or craving-related thoughts, as well as repetitive behaviors such as compulsive alcohol use (Goldstein & Volkow, 2011). Compared to controls, Veterans and civilians with PTSD exhibit hyperactive AMY and hypoactive medial PFC (mPFC) activity (Huang et al., 2014; Pitman et al., 2012), and significant uncoupling between the mPFC and the AMY during symptom provocation and at rest (Sripada et al., 2012). Of interest, individuals with substance use disorders also demonstrate lower PFC-AMY functional connectivity (Gu et al., 2010). Importantly, in a recent study in cocaine-dependent individuals, attenuated PFC-AMY connectivity was shown to be a marker of early relapse risk (McHugh et al., 2014). Another study found that chronic alcohol use generates long-term plasticity in the mPFC and impair fears extinction, suggesting that alcohol may exacerbate the pathophysiology of PTSD or impair recovery from PTSD (Holmes et al., 2012).

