Power. This study is powered to estimate the effects of doxazosin on significant reduction in PTSD symptoms at the end of treatment (see Hypothesis 1), and increased abstinence rates at the end of treatment (see Hypothesis 2). Placebo rates of reduction in CAPS scores are conservatively estimated to be 20% (Zohar et al., 2002). In a small pilot study, De Jong et al. (2010) found ~31% reduction in CAPS scores using 4mg doxazosin. A sample of 100 participants will provide 80% power with a .05 type 1 error rate to detect a difference in the reduction of CAPS scores between doxazosin (31±20%) and placebo (20±20%). Placebo rates of drug abstinence are estimated from established double-blind placebo controlled trials. Continuous abstinence from weeks 9-12 is observed in 10-15% of treatment seekers without co-occurring PTSD (Shorter et al., 2013) so we anticipate an attenuated rate of 5-10% in the placebo group. Although there is limited information on the effectiveness of doxazosin in addiction, a sample of 100 subjects (50 in each arm) will provide adequate power to detect an abstinence rate as low as 32% in the doxazosin when the placebo cessation rate is 10% and as low as 23% when the placebo rate is 5%. Due to the nature of the study population, we anticipate ~30% dropout rate; thus the number of subjects randomized is inflated to 144, n=72 randomized to each treatment arm of the study.

Power calculations for the neuroimaging component are based on previous studies of individuals with PTSD or substance use disorders. Based on our previous work and the extant literature, we conservatively estimate that approximately 88/144 will be eligible and volunteer to participate in the neuroimaging component. Of these 88 participants, half (n=44) will be assigned to doxazosin and half to placebo (n=44). Hypotheses 3A and 3B will, therefore, involve the subset of 44 participants who complete the neuroimaging component and receive doxazosin treatment. A recent study of Veterans with PTSD (n=14) as compared to controls (n=15) observed significant differences in PFC-AMY resting state connectivity (Sripada et al., 2012). The effect size for this difference was 0.8 (measured using Cohen's d). Thus, power (1- β) reaches .80 with a total sample size of N=26 (two-tailed, alpha=.05). Another recent study of cocaine-dependent individuals (N=45) found that

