Hypothesis 2: Participants who receive doxazosin, as compared to placebo, will evidence significantly greater reductions in SUD severity. To test this hypothesis, logistic regression analysis will be used to examine rates of abstinence (TLFB, biological tests) during the end of treatment phase (week 9-12). Weekly point prevalence abstinence will be examined using generalized linear models under a generalized estimating equations (GEE) framework. GEE models will allow for examination of differential effects of doxazosin vs. placebo on abstinence over the course of the treatment phase of the study. Weekly abstinence (yes/no) as well as amounts (e.g., standard drink units, dollar amount of substances) will be examined over time to determine if treatment is effective in reducing substance use when abstinence is not achieved.

Hypothesis 3A: PFC-AMY connectivity at rest and in response to trauma vs. neutral cues will predict amount of change in PTSD symptoms (CAPS-5).

Hypothesis 3B: PFC-AMY connectivity at rest and in response to substance vs. neutral cues will predict time to first use of alcohol or drugs (TLFB).

The following preprocessing and analytical parameters will be used to test hypotheses 3A-3B. **Preprocessing:** Post-acquisition preprocessing and statistical analysis of all of imaging data will be performed using FEAT (fMRI Expert Analysis Tool) Version 5.98, part of FSL (FMRIB's Software Library). Data will be preprocessed using scripting tools from FEAT. Non-brain signal will be removed using FSL's BET brain extraction. Scans will be corrected for motion using FSL's linear registration and scans will be spatially smoothed using a Gaussian kernel of 8 mm FWHM. Participants with head motion ≥ 0.2 mm will be excluded from the analyses [1]. Motion artifacts will be identified and scrubbed from each subject's data. Scans will be spatially co-registered with a standardized anatomical template (Montreal Neurological Institute) using a 12 parameter affine transformation.

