fMRI Analysis: Functional connectivity will be measured using a PPI seed-based approach [2]. PPI analyses for resting state, trauma and substance cues will be performed separately. Customized sq. wave forms representing the trauma run (1=trauma block and -1=neutral block) and the substance cue run (1=substance block and -1=neutral block) the duration of each block will be convolved with a double-gamma hemodynamic response function. A mask of the seed region will be made using a 12-mm diameter sphere located in the center

of the amygdala using the MNI coordinates (x, y, z = ±22, 0, -22). The transformation parameters described above will also be applied to the mask. For each subject, the mean corrected and high pass filtered time series of the BOLD signal in the AMY will be extracted and used in a single subject whole brain PPI analysis. The PPI model will include the task vector, time series of the BOLD signal in the AMY, a term representing the positive task x seed interaction, and a term representing the negative task x seed interaction. The first level analysis will generate contrast images of the parameter estimates for each of the four regressors. Voxels will be thresholded at $Z>2.3$ using a corrected cluster threshold of $p=0.05$. The contrast images of the parameter estimates of the positive and negative task x seed interactions will be combined for group-level t-tests to identify regions that exhibited altered connectivity with the AMY during the trauma and substance cues as compared to neutral cues. All group-level results will be thresholded at $Z>2.3$ using a corrected cluster threshold of $p=0.05$. Separate linear regression tests will be used to test for associations between PFC-AMY connectivity at baseline and improvement in PTSD and SUD symptoms during treatment. Changes in CAPS-5 total scores will be regressed against the parameter estimate obtained from the center voxel from each cluster that exhibited a significant task x seed interaction with the AMY at rest and in response to the trauma cue (Hypothesis 3A). The number of days to first use (TLFB) will be regressed against the parameter estimate obtained from the center voxel from each cluster that exhibited a significant task x seed interaction with the AMY at rest and in response to the substance cues (Hypothesis 3B).

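### Hypothesis 3A regresses CAPS-5 change on connectivity in the doxazosin arm without a baseline CAPS-5 term, so a significant result may only reflect entry severity

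*Combined protocol and SAP*

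**What the plan says.** Hypothesis 3A is that "PFC-AMY connectivity at rest and in response to trauma vs. neutral cues will predict amount of change in PTSD symptoms (CAPS-5"). The fMRI Analysis section gives the model: "Separate linear regression tests will be used to test for associations between PFC-AMY connectivity at baseline and improvement in PTSD and SUD symptoms" during treatment. For 3A it adds that "Changes in CAPS-5 total scores will be regressed against the parameter estimate obtained from the center voxel" of each cluster showing a significant interaction with the amygdala, at rest and under the trauma cue. No covariate is named. The mixed model in the Hypotheses section belongs to Hypothesis 1 and does not cover 3A.

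The Power section says that Hypotheses 3A and 3B "involve the subset of 44 participants who complete the neuroimaging component and receive doxazosin treatment", so no placebo participants enter. The same section expresses the expected CAPS effect as a percent reduction, 31±20% on doxazosin. The Background reports, for people with PTSD compared with controls, "significant uncoupling between the mPFC and the AMY during symptom provocation and at rest". Current PTSD is an inclusion criterion. The section Problems and Alternative Strategies calls the neuroimaging work a secondary objective.

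**The concern.** A change score contains the baseline score. If absolute change is larger in people who start higher, anything correlated with baseline CAPS-5 will also correlate with change. Connectivity could then reach significance while telling a clinician nothing that the baseline interview had not already told. With only the doxazosin arm analysed, no comparison group shows how much of the severity-related change would have occurred anyway.

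This matters for interpretation. The Overview presents imaging as a source of diagnostic and prognostic indicators, and the plan intends the results to guide later studies. A marker that stands in for entry severity would be a poor basis for that.

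**Working it through.** **The plan's own figures.** The documents give no correlation between connectivity and baseline CAPS-5, and none between baseline and week-12 CAPS-5, so there is no stated figure to reproduce on this point. The imaging power statements concern two-group differences (d = 0.8 and d = 1.0), not a regression on change, and do not bear on it.

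**Inputs from the documents.** N = 44, doxazosin arm only; CAPS reduction 31±20%; dropout about 30%. If that dropout also applied to the imaging subset (an assumption), 44 × 0.7 = 30.8, or about 31.

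**Assumed inputs.** r = correlation of connectivity with baseline CAPS-5, 0.2 to 0.4; rho = correlation of baseline with week-12 CAPS-5, 0.3 to 0.7; baseline CV 0.25; CAPS-5 reliability 0.8 to 0.9. The plan does not name the visit that ends the change score; week 12 is assumed.

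**Model 1: outcome and connectivity both depend on the measured baseline, with equal SDs.** If connectivity adds nothing beyond baseline, then

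corr(connectivity, change) = −r × √((1 − rho)/2).

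With rho = 0.5 the root is √0.25 = 0.5, so r = 0.2, 0.3 and 0.4 induce −0.10, −0.15 and −0.20.

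**Model 2: the plan's proportional reduction.** Let change = −p × baseline, where p has mean 0.31 and SD 0.20 and is independent of connectivity, and baseline has mean 1 and SD 0.25. Then E[p²] = 0.31² + 0.20² = 0.1361, and

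corr = −r × 0.31 × CV / √(0.04 + 0.1361 × CV²) = −r × 0.0775 / √0.0485 = −0.352r.

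For r = 0.2, 0.3 and 0.4 this gives −0.07, −0.11 and −0.14. Measurement error was then added at both visits, with the reduction applied to true severity and connectivity linked to true severity.

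**Model 3: stable severity.** Connectivity tracks true severity, CAPS-5 carries random error, and true change does not depend on severity.

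Rejection rates at nominal 5%, N = 44, 20,000 simulated samples per cell:

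| Setting | r = 0.2 | r = 0.3 | r = 0.4 |
|---|---|---|---|
| Model 1, rho 0.3, unadjusted | 12% | 21% | 34% |
| Model 1, rho 0.5, unadjusted | 10% | 17% | 26% |
| Model 1, rho 0.7, unadjusted | 8% | 12% | 17% |
| Model 1, any of these rho, baseline-adjusted | 5% | 5% | 5% |
| Model 2, reliability 0.9, unadjusted | 7% | 9% | 13% |
| Model 2, reliability 0.8, unadjusted | 7% | 9% | 12% |
| Model 2, reliability 0.8 to 0.9, baseline-adjusted | 5–6% | 5–6% | 6–7% |
| Model 3, rho 0.5, unadjusted | 5% | 5% | 5% |
| Model 3, rho 0.5, baseline-adjusted | 12% | 22% | 37% |

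With r = 0 every unadjusted rate is about 5%. With N = 31 and rho = 0.5, Model 1 unadjusted gives 8%, 13% and 19%.

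**The case against.** Four objections have force.

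First, a reader might infer that the documents show connectivity to vary with severity in these participants. They do not. The Background finding and the d = 0.8 in the Power section are differences between people with PTSD and controls. Everyone in this trial has PTSD, and neither source reports a correlation with CAPS-5 within cases. The range 0.2 to 0.4 is an assumption.

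Second, a reader might infer that any link with baseline must pass into the change score, and that adjustment is therefore always the safer test. Model 3 shows otherwise: there the change regression holds 5% and the adjusted model over-rejects. Choosing between change and baseline adjustment for a predictor that was not randomised is a trade-off. Model 3 does require that true change not depend on severity, which sits badly with the plan's percent-reduction assumption. This objection therefore argues against simply replacing one model with the other, not against adding the adjusted model.

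Third, Hypothesis 3A as worded claims only that connectivity predicts the amount of change. If severity drives change and connectivity tracks severity, that claim is literally true. What cannot be claimed from the unadjusted model is information beyond entry severity.

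Fourth, one might extend the argument to Hypothesis 3B. Its outcome is days to first use, which is not a change score, so the mechanism does not apply.

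**Conclusion.** The point holds for Hypothesis 3A in a conditional form. The stated model cannot separate a marker of response from a proxy for baseline CAPS-5. Whether this produces misleading significance depends on two conditions: a within-PTSD link between connectivity and baseline CAPS-5, which is unknown, and dependence of change on baseline, which the plan's effect assumption implies.

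If both hold with r of 0.2 to 0.4 and N = 44, the unadjusted test rejects about 7% to 13% of the time under the proportional-reduction model and about 10% to 26% with rho = 0.5, against a nominal 5%. If there is no link, or under the stable-severity model, there is no inflation. Confidence in the size is moderate at best because the key correlations are assumed. The documents do not support saying that the planned test is invalid in general, nor that the adjusted test alone would be valid. The consequence is confined to a secondary, hypothesis-generating objective; Hypotheses 1 and 2 are unaffected.

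**What to change.** For Hypothesis 3A only:

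- Prespecify the regression of week-12 CAPS-5 on baseline connectivity with baseline CAPS-5 as a covariate.
- Keep the unadjusted change regression as a sensitivity analysis.
- Report the correlation between connectivity and baseline CAPS-5 in the analysed participants.
- Describe connectivity as predictive beyond entry severity only if both models agree.

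Baseline and week-12 CAPS-5 are already scheduled in Table 1, so the cost is SAP wording and one degree of freedom. The drawback is that the adjusted model can itself over-reject when baseline CAPS-5 is noisy, which is why both models are reported. No change to Hypothesis 3B follows from this point.

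### Hypotheses 3A and 3B name prefrontal-amygdala connectivity, but no prefrontal region is predefined, so the predictor may not exist or the outcome regressions may multiply without correction

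*Combined protocol and SAP*

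**What the plan says.** Under Hypotheses, 3B states that "PFC-AMY connectivity at rest and in response to substance vs. neutral cues will predict time to first use". 3A is its counterpart, with trauma cues as the contrast and change in CAPS-5 as the outcome. Each hypothesis therefore covers two conditions, rest and cue.

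The fMRI Analysis paragraph sets out how they are tested:

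- The amygdala seed is fixed in advance, as a 12-mm sphere at stated MNI coordinates. Its signal is "used in a single subject whole brain PPI analysis". No PFC mask, coordinates or boundary are given.
- Group-level t-tests look for regions whose connectivity with the amygdala differs between the trauma or substance cues and the neutral cues. The maps are thresholded at Z above 2.3 with cluster correction at p=0.05.
- "Separate linear regression tests will be used to test for associations between PFC-AMY connectivity at baseline" and clinical improvement. In practice the predictor is "the parameter estimate obtained from the center voxel from each cluster that exhibited a significant task x seed interaction with the AMY", at rest and under the relevant cue.

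No significance level is stated for these regressions, and no adjustment across them.

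The Power section puts 44 participants in the 3A and 3B analyses: the imaging volunteers assigned to doxazosin. Problems and Alternative Strategies describes imaging as a secondary objective meant to inform later research.

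**The concern.** The region in the hypothesis and the rule that produces the predictor do not match, and this matters in three ways.

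First, clusters are selected because the group-mean interaction differs from zero, whereas the hypotheses concern variation between people. A PFC area whose connectivity varies widely around a mean near zero would yield no cluster, and so no test, even if it predicted outcome well.

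Second, each surviving cluster brings its own regression. The number of tests is known only after the data are seen, and nothing limits the overall chance of a false association. The cluster threshold controls false clusters on the maps; it does not control false links between a cluster and CAPS-5 change or days to first use.

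Third, the resting predictor cannot be built as described. The rule asks for a task-by-seed interaction at rest, but the resting scan is six minutes of fixation with no task blocks. The group-level t-tests are described for the cues only.

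At stake is whether a positive or null result for 3A or 3B can be interpreted. Hypotheses 1 and 2 are untouched.

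**Working it through.** **1. The plan's own figures.** The plan states no cluster count, no familywise error and no power for these regressions. Its imaging power statements are for two-group comparisons (80% power, two-tailed 0.05). A two-sample t-test at d=1.0 needs 17 per group, 34 in total, which matches the stated 34. At d=0.8 it needs 26 per group, 52 in total; the stated total of 26 matches the per-group number and as a total gives about 50% power. Neither figure gives the power of a regression in 44 people.

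**2. Familywise error.** Inputs: k regressions, one per surviving cluster (k is not in the plan, so a range is shown), and 0.05 each. The 0.05 is an assumption, borrowed from the imaging power statements. If tests are independent, the chance of at least one false positive is 1 − 0.95^k:

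- k=2: 1 − 0.9025 = 9.8%
- k=5: 1 − 0.7738 = 22.6%
- k=10: 1 − 0.5987 = 40.1%

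The clusters share a seed, a sample and an outcome, so independence is the upper end. Simulating k equally correlated two-sided z-tests (200,000 draws) gives:

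| k | independent | correlation 0.5 | correlation 0.8 |
|---|---|---|---|
| 2 | 9.8% | 9.1% | 7.8% |
| 4 | 18.5% | 15.5% | 11.4% |
| 5 | 22.6% | 18.3% | 12.9% |
| 10 | 40.1% | 28.6% | 17.3% |

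The row k=4 is the case of one cluster in each condition of each hypothesis, if rest yields clusters at all. Each single regression keeps its 5% level, because clusters are selected on the mean effect and not on outcome. It is the rate across the set that rises.

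**3. Price of control.** The smallest correlation detectable with 80% power, by Fisher's z, is r = tanh[(z for alpha/2 + 0.842) / √(n − 3)].

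- n=44, one test at 0.05: tanh[(1.960 + 0.842)/6.403] = tanh(0.438) = 0.41
- n=44, first Holm step at 0.05/2 = 0.025: tanh[(2.241 + 0.842)/6.403] = tanh(0.481) = 0.45

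If the main trial's roughly 30% dropout also applied to the 44 (an assumption), n = 44 × 0.7 ≈ 31, and the two values become 0.485 and 0.525.

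**The case against.** The strongest reply is that the sentence introducing the regressions calls them tests of PFC-amygdala connectivity, and the sentences on individual clusters are tagged to 3A and 3B. On a natural reading only PFC clusters count, so k may be 1 or 2. That is fair. A reader might infer that a cluster outside the PFC could be declared confirmation of 3A or 3B, but the documents contain no such rule, and such a cluster would not fit the wording of the hypotheses. What remains is that the PFC has no stated boundary, several PFC clusters would still be tested without adjustment, and with no PFC cluster there is no predictor.

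A second reply is that the maps are corrected. They are, and the point here concerns only the regressions.

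A reader might also infer that using one center voxel costs precision and weakens the slope. The documents do not support a claim of that kind. The plan says "scans will be spatially smoothed using a Gaussian kernel of 8 mm FWHM". For spatially white noise, a kernel with SD 8/2.355 = 3.40 mm averages over about (4π)^1.5 × 3.40³ ≈ 1,750 mm³. The acquired voxel is (230/64)² × 3.7 ≈ 48 mm³, so this is about 37 voxels. Any remaining loss cannot be sized from the plan, and a mean over an anatomical mask could dilute the signal instead.

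Finally, imaging is called secondary. The Summary of the Protocol under Data Safety and Monitoring does list functional connectivity among the primary outcomes of interest. However, Assessment Instruments names only CAPS-5 and TLFB as primary clinical outcomes, and Problems and Alternative Strategies is explicit. This limits the consequence but does not remove the gap.

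**Conclusion.** The point holds for the definition of the predictor and for multiplicity. As written, 3A and 3B can go untested, or can be tested a number of times that depends on the data and is not corrected. With 0.05 per regression, familywise error is 10%, 23% and 40% for 2, 5 and 10 independent tests, and about 9%, 18% and 29% at correlation 0.5. These figures rest on an assumed level, an unknown cluster count and an assumed dependence; if only one or two PFC clusters survive, the inflation is small. The resting predictor needs a definition in any case. The conclusion does not rest on center-voxel precision or on non-PFC clusters being counted as support. It bears on the interpretation of a secondary objective, not on the efficacy analyses.

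**What to change.** Amend the fMRI Analysis paragraph before the imaging data are analyzed:

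- Predefine one PFC region for 3A and 3B. The sponsor should choose a mask consistent with the hypothesis and record it.
- Extract one connectivity estimate per participant per condition from that region: the cue-versus-neutral interaction for the cue runs, and plain seed-to-region connectivity for rest.
- State the significance level, and apply Holm across rest and cue within each hypothesis. This holds each hypothesis at 0.05, and the two together at no more than 0.05 + 0.05 = 0.10.
- Report all other clusters as exploratory.

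The scans and software do not change. The costs are SAP wording, a rise in the detectable correlation at n=44 from about 0.41 to 0.45 for the first Holm step, and the loss of confirmatory status for any effect outside the chosen region.

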- Time Line Follow-[name] (TLFB; Sobell & Sobell, 1992): The TLFB obtains retrospective self-report of substance use by using a calendar and memory prompts to stimulate recall. Quantity and frequency assessments are made using this instrument (e.g., total number of standard drink units, percent of days using) as well as abstinence (yes/no). TLFB yields consistently high test-retest correlations and correlates well with other self-reports and collateral reports. The TLFB will assess consumption of alcohol (standard drink units) and drugs for 60 days prior to starting the study, during the treatment and follow-up phase.
- Alcohol Breathalyzer Test will be used to measure subjects' blood alcohol concentration (BAC) when they come into the clinic. Samples reading >0.01 g/dl will be considered positive.
- Alcohol Use Disorders Identification Test (AUDIT; Babor et al., 2001): The AUDIT is a 10-item self-report screening measure, developed by the World Health Organization (WHO), with three subscales (alcohol consumption, drinking behavior, and alcohol-related problems). Items are summed for a total score of 40. The AUDIT has good internal consistency (α = .80-.93) as well as sensitivity and specificity.
- Addiction Severity Index—Family History Subscale; (Cacciola et al., 2007; McLellan et al., 1992): The ASI—Family History Subscale is a standardized, semi-structured interview that provides information regarding family history of drinking and drug use and treatment history.

- Quick Drinking Screen (QDS) self-report version. The QDS (Sobell et al., 2003) will be used to measure alcohol consumption. It consists of 4 items probing frequency and quantity of alcohol consumption. It will be administered in a self-report form. The QDS has been validated against the Timeline Followback daily estimation measure of alcohol use, and it shows good psychometric properties (Roy et al., 2008; Sobell et al., 2003). The QDS's time-frame will be modified to match the "last two weeks" probed by the mandated depression and anxiety instruments for CAP studies (PHQ-9 and GAD-7). Like these other measures, the QDS can be administered frequently throughout CAP trials to track changes in alcohol use.

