individuals who relapsed (n=24) during treatment had significantly lower PFC-AMY connectivity at baseline as compared to individuals who did not relapse (n=21) (McHugh et al., 2014). The effect size for this reduction was 1.0. Thus, power (1- β) reaches .80 with only 34 total participants (two-tailed, alpha=.05). The present study is therefore well-powered to test the proposed hypotheses.

Missing Data. We will perform attrition analyses on whether participants and dropouts differ on key variables, and whether variables on which they differ interact with treatment to affect outcome measures. As participants will be randomized to treatment, it is unlikely that missing data will produce biased estimates of treatment effect, as observed and unobserved covariates should theoretically be balanced across treatment groups. In addition, in general, less than 10% missing data have little impact on power and do not introduce bias, regardless of the missing data mechanism. Larger proportions of data missing at random (MAR) or missing not at random (MNAR) could potentially bias study findings and reduce power. If the percent missing data are greater than 10%, propensity score methods will be used for data imputation. In the propensity score method, first the distribution of the missing indicator variable given the observed data is modeled to derive a propensity score. Then observations are grouped on these propensity scores and an approximate Bayesian bootstrap imputation is applied to each group.

Hypotheses. The hypotheses and statistical approaches for testing each hypothesis are listed below. An experienced biostatistician at MUSC ([name], Department of Public Health) who has worked with our group for the past five years will collaborate with [name] (Director of the CAP Data Management and Biostatistics Core) as needed during the project to ensure consistency across sites with regard to scoring and analysis of dependent measures.

Hypothesis 1: Participants who receive doxazosin, as compared to placebo, will evidence significantly greater reductions in PTSD severity. To test this hypothesis, generalized linear mixed effects models will be employed to assess reduction in CAPS-5 and PCL-5 total scores during the treatment phase. Restricted maximum likelihood (REML) methods will be used to estimate the fixed effects and variance components, and model based treatment effect estimates will be used to construct group level tests over time.

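### Hypothesis 3B concerns time to first use, but the plan tests it by linear regression of days to first use and gives no rule for participants who never use

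*Combined protocol and SAP*

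**What the plan says.** Under Hypotheses, 3B states that connectivity at rest and in response to substance versus neutral cues "will predict time to first use of alcohol or drugs (TLFB"). The fMRI Analysis section names the method for both imaging hypotheses: "Separate linear regression tests will be used to test for associations between PFC-AMY connectivity at baseline and improvement in PTSD and SUD symptoms". For 3B specifically: "The number of days to first use (TLFB) will be regressed against the parameter estimate obtained from the center voxel from each cluster" that showed a significant interaction with the amygdala.

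The related text elsewhere is:

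- **Power, analysis set.** Hypotheses 3A and 3B "involve the subset of 44 participants who complete the neuroimaging component and receive doxazosin treatment".
- **Power, evidence for 3B.** In a cited study of 45 cocaine-dependent people, "individuals who relapsed (n=24) during treatment had significantly lower PFC-AMY connectivity at baseline as compared to individuals who did not relapse (n=21"), with an effect size of 1.0.
- **TLFB coverage (Assessment Instruments).** Alcohol and drug use is recorded for "drugs for 60 days prior to starting the study, during the treatment and follow-up phase".
- **Missing Data.** "If the percent missing data are greater than 10%, propensity score methods will be used for data imputation"; after grouping on the scores, "an approximate Bayesian bootstrap imputation is applied to each group".
- **General.** Analyses are on the intent-to-treat sample of all randomized subjects.

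The plan does not mention censoring, a survival model, or a value for a participant with no first use.

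**The concern.** Days to first use exists only for someone who used. For a participant abstinent throughout treatment, the data show only that first use, if any, came after the end of observation. Linear regression needs a number, and the plan does not supply one.

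The variable is also not fully defined. No day zero is given. The end of the window is open as well: the fMRI Analysis section speaks of improvement during treatment, while the TLFB continues into follow-up.

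These participants carry much of the information. The plan's own evidence for 3B is a contrast between people who relapsed and people who did not. If never-users are left out, one side of that contrast disappears, the association shrinks and power falls. If the choice is made after the data are seen, the 3B result depends on an analyst's decision.

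**Working it through.** **1. The plan's own figure.** The only power statement bearing on 3B is 34 participants in total for power .80 at effect size 1.0, two-tailed alpha .05. A two-sample t test with d = 1.0 and 17 per group (2 × 17 = 34) has power 0.807, so the figure reproduces. It describes a comparison of two group means, not a regression of days to first use and not a time-to-event model.

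**2. How many participants have no first-use day.** The plan gives no never-use rate, so a range is needed.

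- 5–10% are the abstinence rates the Power section expects on placebo in weeks 9–12.
- 32% is a detectable doxazosin rate for weeks 9–12 in the same section; 20% is an intermediate value.
- 21/45 = 47% is the share without relapse in the cited study.

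Abstinence in weeks 9–12 is not the same as never using, so these values are assumptions. Among 44 participants they give 44 × 0.05 = 2.2, 44 × 0.10 = 4.4, 44 × 0.20 = 8.8, 44 × 0.32 = 14.1 and 44 × 21/45 = 20.5 without a first-use day.

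**3. Model.** Connectivity x is standard normal, and time to first use is exponential with hazard λ·exp(−βx). The window is 12 × 7 = 84 days, n = 44, with no dropout. For each never-use share q, λ is solved from q = E[exp(−84·λ·exp(−βx))]. The effect is calibrated to the plan: at q = 21/45, β = 0.764 per SD gives a standardized difference in connectivity of 1.00 between those without and with an event.

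**4. Power, two-sided .05** (simulation, thousands of replicates per setting, accurate to about 0.01).

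| Never-use | Cox, censored at day 84 | Linear, users only | Linear, never-users at day 84 | Fall in slope, users only |
|---|---|---|---|---|
| 5% | 0.99 | 0.91 | 0.98 | 30% |
| 10% | 0.98 | 0.80 | 0.97 | 38% |
| 20% | 0.98 | 0.58 | 0.97 | 48% |
| 32% | 0.97 | 0.34 | 0.96 | 54% |
| 47% | 0.93 | 0.16 | 0.89 | 61% |

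The slope column compares users-only regression with regression on days within the 84-day window for all participants.

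**5. A weaker effect** (log hazard ratio 0.5 per SD, assumed), at the same never-use rates:

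- Cox: 0.84, 0.83, 0.79, 0.73, 0.65
- Users only: 0.61, 0.46, 0.27, 0.15, 0.09
- Last-day coding: 0.82, 0.81, 0.76, 0.68, 0.57

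**6. No effect.** All three methods reject at close to 5% (0.047 to 0.059). The harm is attenuation and lost power, not false positives.

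**The case against.** Four points on the other side have weight.

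- **A sensible analyst would keep never-users.** The intent-to-treat sentence points that way, and last-day coding then loses only 1–4 points against Cox at the calibrated effect. This stands as far as it goes. But that sentence is not a coding rule, and 3B already uses an imaging subset of one arm. The plan still does not say what value a never-user receives.
- **Never-use may be rare.** Entry requires a current substance use disorder, with no stated abstinence requirement. At 5–10% and the calibrated effect, even users-only regression has power 0.91–0.80. That is fair; the slope is nevertheless 30–38% too small.
- **Cox has its own weakness.** Suppose 30% of the sample left unobserved just before first use. Cox power would then run from 0.94 at 5% never-use to 0.57 at 47%, against 0.98 to 0.89 for last-day coding. This is why the fix includes a sensitivity analysis.
- **3B serves a secondary objective** (Problems and Alternative Strategies), meant to inform future research. That limits the weight of the point.

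A reader might go further and infer that the imputation rule would assign abstinent completers a first-use day they never had. The documents do not support this. A completer who never used has a full TLFB record, so nothing is missing. At most the rule could concern participants who leave while abstinent.

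A reader might also apply the anticipated dropout of about 30% to this analysis. If completing the neuroimaging component includes the second scan, which the Figure 4 caption places in week 12, early leavers are largely outside the 44.

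**Conclusion.** The gap is real. A time-to-event hypothesis is tested by a method that needs an observed day for everyone, and the plan defines neither the origin, nor the window, nor the handling of participants without use.

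The cost depends on the handling. It is small under last-day coding: 1–4 points of power at the calibrated effect and 2–8 points at the weaker one. It is severe if never-users are dropped and they make up 20% or more. The severe figures should not be read as what the plan will produce, because the plan does not say never-users are dropped and the intent-to-treat sentence weighs against it.

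The figures rest on exponential times, an 84-day window, n = 44, no dropout and an assumed never-use rate. Hypotheses 1 and 2 are unaffected. This is a cheap improvement that should be made, and no more than that.

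**What to change.** In the fMRI Analysis section, limit the linear regression sentence to Hypothesis 3A. For 3B, keep the connectivity predictor as stated and write along these lines:

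*Days to first use of alcohol or drugs (TLFB) are counted from first dose to the end of the 12-week treatment phase and analysed with a Cox model. Participants without use are censored at the end of treatment, or at the last TLFB-covered day if earlier. The missing-data imputation is not applied to these times. The hazard ratio per SD with 95% CI, the number of first uses and the number censored will be reported.*

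Say openly that the origin and window are new choices that fill a gap in the plan.

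Add one prespecified sensitivity analysis that counts anyone who leaves while abstinent as using on the day after the last TLFB-covered day. In the informative-dropout scenario above, it restores power to 0.99 at 5% never-use and 0.93 at 47%.

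If linear regression is kept, the acceptable minimum is one sentence: all participants stay in, and those without use are coded at the last TLFB-covered day up to the end of treatment.

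The cost is a few sentences, with the same data and standard software. The downside is reliance on proportional hazards and non-informative censoring.
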